### **3.5.2 Software**

All statistical summaries and analyses of safety and immunogenicity data will be performed using SAS® 9.4 or higher (Statistical Analysis System, SAS-Institute, Cary, NC, USA) on a Windows 2016 server.

### **3.5.3 Disposition of Subjects**

All subjects screened will be accounted for.

A summary table will be presented specifying:

- The number of subjects screened (i.e., signed informed consent)
- The number of subjects randomized
- The number of subjects vaccinated (i.e., receiving at least 1 of 2 vaccinations)
- The number and percentage of subjects eligible for the full analysis set (FAS)
- The number and percentage of subjects eligible for the per-protocol analysis set (PPS)
- The number and percentage of subjects eligible for the immunogenicity analysis set (IAS)

An additional summary table will be presented specifying:

- The number of subjects vaccinated (i.e., receiving at least 1 of 2 vaccinations)
- The number of subjects who never received any vaccination
- The number of subjects who received only the first vaccination
- The number and percentage of subjects who received both vaccinations.
- The number and percentage of subjects who completed the active trial phase (i.e., have a disposition event in the database designated as “ACTIVE COMPLETED”)
- The number and percentage of subjects withdrawn from the second vaccination before Visit 3 as well as the frequency and percentage of the reason for withdrawal from second vaccination
- The number and percentage of subjects prematurely discontinuing from the trial before EAP as well as the frequency and percentage of the reason for withdrawal from the trial
- The number and percentage of subjects attending FU1
- The number and percentage of subjects attending FU2
- The number and percentage of subjects who discontinued from the Follow Up Phase as well as the frequency and percentage of the reason for withdrawal from the Follow Up Phase

The percentages will be based on the number of subjects who received at least one vaccination.

A listing will present for all subjects in FAS the following:

- Completion Status for the Active Trial Phase (Yes/No)
- If completion status is No, then the listing will present the Trial Premature Discontinuation Date, Day and Reason
- Receipt (Yes/No) and date of first and second vaccination
- If the second vaccination was not received, then the listing will present the reason
- Completion of FU1 and FU2 (Yes/No)

A listing will present all violations of the inclusion criteria for the FAS. Similarly, a listing will present all exclusion criteria fulfilled for the FAS.

### **3.5.4 Demographic and Other Baseline Data**

#### **Demographics**

Descriptive statistics for the demographics will be produced for the FAS, PPS, and IAS. Continuous variables include: age at screening (years), height at screening (cm), weight at screening (kg) and BMI at screening (kg/m^2). If there is a full rescreening then the information from the rescreening visit will be used.

Age is presented as captured in the SDTM Subject Characteristics (SC) domain. Age is auto-calculated from the eCRF where age is calculated as the difference between informed consent date and date of birth converted to years using the Joda-Time Java API and ISO8601 calendar system.

Frequencies and percentages of subjects will be tabulated for the categorical variables gender, race and ethnicity in the same table by treatment group and overall. Percentages will be based on the total number of subjects in each table pertaining to the FAS, PPS, or IAS.

The demographic listing will be presented for the FAS.

#### **Medical History**

A summary of medical history by SOC and PT per MedDRA 19.1 will be produced by treatment group for the FAS.

A medical history listing will be presented for the FAS.

#### **Vaccine Assessment at Screening**

A listing of vaccine history and planned vaccination at screening will be presented for all subjects.

### **3.5.5 Prior and Concomitant Medications**

All prior medication will be listed by Anatomical-Therapeutic-Chemical (ATC) class Level 2, Level 3, PT and Generic name per the September 2016 version of World Health Organization Drug Dictionary (WHO-DD) for the FAS population. The listing “Prior medication” includes the medication data where end date is before date of first administration of trial vaccine.

All Concomitant Medication will be summarized by ATC class Level 2 and Level 3 for all subjects in the FAS. A concomitant medication listing will also be presented for the FAS. The table and listing “Concomitant Medication” includes ongoing medication or medication with missing end date or with end date after date of first administration of trial vaccine, as well as medication starting after first administration.

All listings will display the original dates as captured in the eCRF.

### **3.5.6 Compliance**

Compliance will be summarized for the FAS population with respect to:

- Number of subjects who received at least one vaccination
- Number and percentage of subjects who received vaccination 1
- Number and percentage of subjects with memory aid returned at vaccination 1
- Number and percentage of subjects who received vaccination 2
- Number and percentage of subjects with memory aid returned at vaccination 2
- Number and percentage of subjects who received both vaccinations

Separate listings for vaccine administration and memory aid will also be presented.

### **3.5.7 Immunogenicity Analysis**

#### **ELISA, PRNT and ELISPOT**

All serum and nasal swab immunogenicity results will be listed for the FAS. Tables will be prepared for the FAS and the PPS. Immunogenicity results from PBMC samples will be summarized for the IAS population.

#### **Primary immunogenicity endpoint: PRNT (A strain) titers**

The primary analysis of the primary endpoint is Geometric Mean Titers (GMTs) after one or two MVA-BN-RSV vaccinations or placebo measured by Plaque Reduction Neutralization Test (PRNT; against strain A) 2 weeks post last vaccination.

The primary immunogenicity endpoint will also be summarized descriptively using the geometric mean of fold increase, positivity rates (including associated 95% CI's), and response rates (including associated 95% CI's) for each treatment group, and by age group at each sampling point.

In addition, the following descriptive comparison of the ratios of the GMTs and GMFI's between treatment groups by visit will be calculated along with the corresponding 95% CI by assuming that the  $\log_{10}$  PRNT (A strain) titers and  $\log_{10}$  PRNT (A strain) Fold Increases are normally distributed:

1. Group 2 / Group 1 – Two vaccinations compared to one vaccination using Dose 1
2. Group 4 / Group 3 – Two vaccinations compared to one vaccination using Dose 2
3. Group 3 / Group 1 – Dose 2 compared to Dose 1 using one vaccination
4. Group 4 / Group 2 – Dose 2 compared to Dose 1 using two vaccinations
5. Group 2 / Group 5 – Two vaccinations using Dose 1 compared to Placebo
6. Group 4 / Group 5 – Two vaccinations using Dose 2 compared to Placebo

As a secondary descriptive analysis for the primary immunogenicity endpoint, an ANOVA model (with dose and age group as independent variables) of the  $\log_{10}$  titers for the three doses

using Group 2, Group 4, and Group 5 will be performed. For Group 5 (2 vaccinations of Placebo), a dose value of 1 will be used to facilitate the log transformation of the dose. The dose response relationship will be explored in this analysis using linear and quadratic orthogonal contrasts. If the linear contrast (i.e. slope) of the regression fit is significant at the standard significance level of 0.05 then a dose response relationship will have been demonstrated. If the quadratic contrast is significantly different from zero then this will indicate that the dose response is not linear within the dose range used in this trial. Assuming the quadratic effect is negative over the higher dose ranges, then this will be seen as confirmation of a plateau effect in terms of responses for higher dose. This dose response ANOVA will be performed a second time without age group in the model.

As an exploratory analysis, an ANOVA will be conducted on the  $\log_{10}$  titers using dose (2 levels), the number of vaccinations (2 levels), and age group (2 levels) as main effects, and dose-by-number of vaccinations as an interaction term. The main effect of dose (2 levels) will not include the placebo treatment group. To further explore whether baseline titers have an effect on dose, a similar ANOVA will be performed where the dependent variable of  $\log_{10}$  titers will be replaced with  $\log_{10}$  Fold Increase.

All ANOVAs will be performed on the FAS only.

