**Fold Increase**

The fold increase is defined as a subject's post-Baseline titer at Visit X, divided by the baseline titer.

Study specific version: 1.0  
Study specific version Date: 31-May-17

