Recruitment into the trial is performed in a staggered manner. The staggering process is performed at one clinical trial site. The trial starts with a sentinel cohort with a total of 2 subjects, 1 subject recruited into Group 2 and one subject into Group 4 (i.e. 1:1 subjects receiving Dose 1 and Dose 2). Following a positive safety assessment for the subjects in the sentinel cohort, recruitment in the safety cohort starts. The safety cohort includes a total of 10 subjects, 5 subjects each into Groups 2 and 4 (i.e. 5:5 subjects receiving Dose 1 and Dose 2). Following a positive safety assessment for the subjects in the safety cohort, recruitment in all groups for the remaining subjects is opened. The open recruitment phase includes all treatment groups. The open recruitment phase randomization is stratified by age and site.

PBMC collection is performed in a subgroup of 20 subjects in each treatment group (total of 100 subjects). This subgroup also has an additional serum and nasal swab sample collection time point one week post each vaccination in addition to the serum and nasal swab sample collection time points scheduled for all subjects.

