#### **Secondary immunogenicity endpoints**

All other immunogenicity results (PRNT strain B, ELISPOT, ELISA IgG/IgA) will be considered as secondary descriptive analyses and will be analyzed similarly to the primary endpoint analysis (by age group results will be included for ELISA IgA only). Note that for secondary immunogenicity endpoints, ANOVAs will be performed only for PRNT strain B, IgA ELISA and IgG ELISA Total. The dose-response ANOVAs will be performed without age group in the model.

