| 14.2.1.17     | Serum RSV-specific PRNT Strain A: Dose-Response ANOVA Results With Age Group in Model – FAS             |
| 14.2.1.18     | Serum RSV-specific PRNT Strain A: Dose-Response ANOVA Results Without Age Group in Model – FAS          |
| 14.2.1.19     | Serum RSV-specific PRNT Strain A: Exploratory Titer ANOVA Results – FAS                                 |
| 14.2.1.20     | Serum RSV-specific PRNT Strain A: Exploratory Fold Increase ANOVA Results – FAS                         |

Study specific version: 1.0  
Study specific version Date: 31-May-17

|               |   |
|---------------|---|
|               |   |
| 14.2.2 | Serum RSV-specific PRNT Strain B   |
| 14.2.2.1      | Serum RSV-specific PRNT Strain B: Geometric Mean Titer – FAS                    |
| 14.2.2.2      | Serum RSV-specific PRNT Strain B: Geometric Mean Titer – PPS                    |
| 14.2.2.3      | Serum RSV-specific PRNT Strain B: Fold Increase – FAS                           |
| 14.2.2.4      | Serum RSV-specific PRNT Strain B: Fold Increase – PPS                           |
| 14.2.2.5      | Serum RSV-specific PRNT Strain B: Positivity Rates – FAS                        |
| 14.2.2.6      | Serum RSV-specific PRNT Strain B: Positivity Rates – PPS                        |
| 14.2.2.7      | Serum RSV-specific PRNT Strain B: Response Rates – FAS                          |
| 14.2.2.8      | Serum RSV-specific PRNT Strain B: Response Rates – PPS                          |
| 14.2.2.9      | Serum RSV-specific PRNT Strain B: Group Geometric Mean Titer Ratios – FAS       |
| 14.2.2.10     | Serum RSV-specific PRNT Strain B: Group Geometric Mean Titer Ratios – PPS       |
| 14.2.2.11     | Serum RSV-specific PRNT Strain B: Dose-Response ANOVA Results – FAS             |
| 14.2.2.12     | Serum RSV-specific PRNT Strain B: Exploratory Titer ANOVA Results – FAS         |
| 14.2.2.13     | Serum RSV-specific PRNT Strain B: Exploratory Fold Increase ANOVA Results – FAS |
|               |   |
| 14.2.3 | RSV-specific IgA ELISA (serum)   |
| 14.2.3.1      | Serum RSV-specific IgA ELISA: Geometric Mean Titer – FAS                        |
| 14.2.3.2      | Serum RSV-specific IgA ELISA: Geometric Mean Titer – PPS                        |
| 14.2.3.3      | Serum RSV-specific IgA ELISA: Geometric Mean Titer by Age Group – FAS           |
| 14.2.3.4      | Serum RSV-specific IgA ELISA: Geometric Mean Titer by Age Group – PPS           |

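### The fold-increase ANOVA is given the purpose of exploring a baseline-titer effect, but it has no baseline term and cannot show whether the dose effect depends on baseline titer.

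*SAP*

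**What the plan says.** For PRNT strain A, main SAP section 3.5.7 plans an exploratory ANOVA of log10 titers "using dose (2 levels), the number of vaccinations (2 levels), and age group (2 levels) as main effects", with "dose-by-number of vaccinations as an interaction term". Placebo is left out: "The main effect of dose (2 levels) will not include the placebo treatment group". The next step is introduced as follows: "To further explore whether baseline titers have an effect on dose, a similar ANOVA will be performed where the dependent variable of" log10 titer gives way to log10 fold increase. Nothing else in the model changes.

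The General Definitions state: "The fold increase is defined as a subject's post-Baseline titer at Visit X, divided by the baseline titer". Baseline therefore enters only through the outcome. It is not a covariate, a stratum or part of an interaction. Section 3.6, which lists departures from the protocol, adds only age group to these models.

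The approach extends to other assays: "ANOVAs will be performed only for PRNT strain B, IgA ELISA and IgG ELISA Total". Four tables result: 14.2.1.20 ("Serum RSV-specific PRNT Strain A: Exploratory Fold Increase ANOVA Results") and its counterparts 14.2.2.13, 14.2.3.17 and 14.2.4.13. No table in the main SAP splits results by baseline titer. The one table in the documents that does so is 15.2.7.5 in the booster SAP, for mucosal IgA response rates, and it does not cover this analysis.

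**The concern.** The protocol's introduction to RSV disease says that adults have met RSV before and that vaccination is expected to boost an existing, incomplete response. Whether the higher dose adds as much in people with high starting titers as in those with low ones is therefore a sensible exploratory question in a dose-ranging trial. It concerns the variation of the dose effect with baseline, and the term that measures this is dose by baseline titer. Neither planned ANOVA has it.

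The risk is one of interpretation. If the fold-increase ANOVA gives a different dose result from the titer ANOVA, the stated purpose invites the reader to call that a baseline effect. If the two agree, it invites the conclusion that baseline does not matter. Neither inference follows.

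**Working it through.** **The plan's own figure.** No figure is given for the exploratory ANOVA. The main sample size is used here only as a source of inputs, and it reproduces (two-sided 0.05 assumed): log10(1.66) = 0.2201, so n = 2 × (1.960 + 0.842)² × 0.46² / 0.2201² ≈ 69 per group against 70 stated. Power at 70 is 0.81. Four active groups of 70 give 280 evaluable subjects.

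**The identity.** Write y for log10 post-vaccination titer and b for log10 baseline titer, so log10 fold increase is y − b. Least-squares coefficients are linear in the outcome. With the same subjects and design matrix,

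dose coefficient (y − b) = dose coefficient (y) − dose coefficient (b).

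The last term is the adjusted baseline difference between doses. Allocation is random ("The open recruitment phase randomization is stratified by age and site"), so its expectation is zero. As an illustration, if the titer ANOVA gave 0.10 and Dose 2 subjects happened to start 0.03 higher, the fold-increase ANOVA would give 0.07. The 0.03 is chance imbalance and carries no information on whether the dose effect varies with b.

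**Simulation check.** There were 3,000 runs per scenario, with group sizes 78, 89, 80 and 90 (booster SAP Table 2) and titer SD 0.335 (protocol section 9.2). Assumed, and not in the documents: baseline SD 0.32, mean dose effect 0.10 log10, slope of post-vaccination titer on baseline 0.5, 0.7 or 0.9, and dose-by-baseline slope 0, +0.3 or −0.3.

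- The identity held in every run to about 1e-16.
- The mean dose effect was 0.099 to 0.101 in both ANOVAs in every scenario, including those with a true interaction.
- With no interaction, the two ANOVAs disagreed on dose significance in 22.1, 20.9 and 20.6% of runs at baseline slopes 0.5, 0.7 and 0.9.
- Precision for dose, with no interaction:

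| Baseline slope | SE, titer ANOVA | SE, fold-increase ANOVA | SE, baseline as covariate |
|---|---|---|---|
| 0.5 | 0.037 | 0.037 | 0.032 |
| 0.7 | 0.037 | 0.029 | 0.027 |
| 0.9 | 0.037 | 0.019 | 0.019 |

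**What an interaction term could detect.** With equal doses, the SE of the dose-by-baseline slope is about 2 × residual SD / (baseline SD × √n). Take n = 280 and baseline SD 0.30. The baseline SD is an assumption. Back-calculation from the PRNT A baseline intervals in protocol Table 11 gives about 0.28 to 0.32 in the three vaccine groups (n = 18 each) and 0.19 in placebo (n = 9). Where a total SD is given, residual SD = √(total SD² − (0.5 × 0.30)²), with an assumed baseline slope of 0.5. Power is two-sided at 0.05.

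| Scenario | Residual SD | SE of slope | Power at −0.2 / −0.3 / −0.4, formula | Same, simulated |
|---|---|---|---|---|
| Residual SD 0.25 (assumed) | 0.250 | 0.100 | 52 / 85 / 98% | 51 / 85 / 97% |
| Total SD 0.335 (booster planning) | 0.300 | 0.119 | 39 / 71 / 92% | 38 / 67 / 91% |
| Total SD 0.46 (main planning) | 0.435 | 0.173 | 21 / 41 / 64% | 20 / 41 / 62% |

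With no interaction in the data, the re-derived interaction test rejected in 4.8 to 5.5% of runs.

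**The case against.** The best reply is that the sentence need not be about effect modification. Dose is assigned, so baseline cannot literally affect it, and the SAP never mentions an interaction with baseline. A natural alternative reading is whether the dose result changes once each subject's starting titer is taken into account. Changing only the outcome fits that reading, and so does the SAP's presentation of GMT and fold-increase ratios side by side. On that reading the pair of ANOVAs does respond, because their difference is exactly the realised imbalance. This stands as a point about wording. It does not rescue the choice of model: fold increase fixes the baseline slope at 1, while a covariate estimates it and was at least as precise in every scenario above.

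A reader might also infer that the fold-increase ANOVA is redundant. It is not. In any one dataset it can differ from the titer ANOVA, and it is more precise when titers track baseline closely.

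A reader might infer that the dose conclusion is compromised. The documents do not support that. The SAP labels the analysis exploratory, testing is descriptive, no decision rule uses the result, and the table titles make no claim about baseline.

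Lastly, an interaction model might be expected to settle the question. With all 320 recruited subjects and a residual SD of 0.25, simulated power is 58, 88 and 99%. But that residual SD is not in the documents, and 320 ignores the planned dropout. The table above shows how far power falls.

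**Conclusion.** The point holds as one about an exploratory analysis. The fold-increase ANOVA cannot show whether the dose effect depends on baseline titer, and the difference between it and the titer ANOVA reflects chance imbalance only. The algebra needs the same subjects in both models; anyone with a missing Visit 1 titer drops out of the fold-increase model alone. The zero expectation rests on random allocation. The 12 staggered subjects were split equally between the doses, but the documents do not say how each was allocated.

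The mean dose effects, the disagreement rate of about 21 to 22% and the power figures rest on the assumptions listed. The identity does not. The primary GMT comparison is untouched. The booster SAP cites a main-study SAP Addendum of October 11, 2017 that was not available, so a change made there cannot be excluded.

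**What to change.** In SAP section 3.5.7, replace the sentence with a model of log10 titer 2 weeks after the last vaccination (V4) on dose, number of vaccinations, their interaction, age group, centred log10 Visit 1 titer, and dose by centred log10 Visit 1 titer. Report the interaction slope with its 95% CI, and the Dose 2/Dose 1 GMT ratio at the 25th and 75th percentiles of Visit 1 titer. Do the same for PRNT strain B, IgA and total IgG. Keep the fold-increase ANOVA as a description of fold increase, without the stated purpose. If only sensitivity to baseline was meant, say so and use the baseline covariate without the product term.

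The cost is a change of SAP wording, two model terms on data already scheduled for collection, and a table layout per assay. The downside is limited power: at the planning SD even a slope of −0.4 would be missed in more than a third of trials. State in advance that a null interaction is to be read through its CI and not as absence of effect modification. The booster SAP records that the main study has been unblinded. If the model is added after analysis, it should be flagged as unplanned, as the SAP's opening section requires.

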#### **Secondary immunogenicity endpoints**

All other immunogenicity results (PRNT strain B, ELISPOT, ELISA IgG/IgA) will be considered as secondary descriptive analyses and will be analyzed similarly to the primary endpoint analysis (by age group results will be included for ELISA IgA only). Note that for secondary immunogenicity endpoints, ANOVAs will be performed only for PRNT strain B, IgA ELISA and IgG ELISA Total. The dose-response ANOVAs will be performed without age group in the model.

#### Geometric Mean Titers (GMTs)

For all ELISA and PRNT results the GMTs will be calculated by taking the antilogarithm of the mean of the  $\log_{10}$  titer transformations.

Descriptive statistics will be derived by visit including number of observations, Min, median, Max, GMT, with 95% CI (derived by the antilogarithm of 95% CI of the  $\log_{10}$  titer transformations based on the percentiles of the t-distribution).

#### Geometric Mean Spot Forming Units (ELISPOT)

SFU/1  $\times 10^6$  PBMC will be reported as whole numbers. Min and Max will be reported as whole numbers. Medians, GMSFUs, and CI will be reported to one decimal place.

A non-parametric percentile based CI ([Hahn](#) G and Meeker W (1991) *Statistical Intervals: A Guide for Practitioners*, New York: John, 1991) will be placed around the median for each treatment group, using the SAS

UNIVARIATE Procedure, i.e.:

```
PROC UNIVARIATE DATA=<dataset_name> CIPCTLDF;  
  VAR <SFU Variable>;  
  BY <Treatment Group variable>;  
  RUN;
```

The calculation of the 95% CI for the Geometric Means will be based upon the assumption that the logarithm of the SFU has a normal distribution.

#### Seropositivity rates

RSV-specific ELISA and PRNT seropositivity rates will be presented by treatment group for each visit along with the Clopper-Pearson 95% CIs.

